4.2.2 Phase 2 Study Endpoints

Phase 2 Primary Endpoint:

- Area Under the Curve (AUC), Sensitivity, and Specificity of VCI when compared against standard of care CTA imaging for large vessel occlusion assessment.

Phase 2 Secondary Technical Efficacy Endpoint:

- Area Under the Curve (AUC), Sensitivity, and Specificity of a novel machine learning (ML) algorithm when compared against standard of care CTA imaging for large vessel occlusion assessment.

- VCI and experimental ML algorithm compared to prehospital/neurological clinical scales for alternative diagnostic criteria.

Phase 2 Primary Safety Endpoint:

- Incidence of device-related serious adverse events
- Last Known Normal (LKN) to First Hospital Arrival (Initial Door-In) time
- Door to Initial CT imaging (non-contrast) time
- Door to IV-tPA time
- Door to Initial CTA Acquisition time
- Door to Groin Puncture time
- CTA Acquisition to Groin Puncture time

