In this work, we will also measure “Get with the Guidelines, Stroke” metrics from each site and compare them to literature, national and site metrics. This will enable us to demonstrate that the system does not adversely affect standard of care for subjects suspected of stroke. The reason we believe it will not affect standard of care is because the device will be used after initial CT and IV-tPA is administered, while the subject is waiting for CTA or intervention. The time window, although short, is available to allow us to measure both the TCD waveform and CTA to confirm VCI is an effective biomarker. Additionally, the times will be compared against the randomized groups (Cohort C and D).

Door to diagnostic imaging. (Statistical demonstration that show we will not delay anything when adding our NovaGuide workflow to), e.g. “Get with the Guidelines, Stroke”: We will calculate the following for subjects that have NovaGuide measurements:

- IV rt-PA arrive by 2 hour, treat by 3 hour: Percent of acute ischemic stroke patients who arrive at the hospital within 120 minutes (2 hours) of time last known well and for whom IV t-PA was initiated at this hospital within 180 minutes (3 hours) of time last known well.
- % Door to CT \leq 25 minutes: Percent of patients who receive brain imaging within 25 minutes of arrival.
- Door to Puncture (DTP) Time within 90 minutes: (Percentage of patients with acute ischemic stroke who receive mechanical endovascular reperfusion)

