11.2 Phase 2 Statistical Analysis

Primary Endpoint Analysis: Demonstration of VCI biomarker performance at or exceeding 90% ROC-AUC (targeting SEN & SPE greater than 90%) to standard of care imaging across multiple centers.

Here, we will determine the final biomarker performance using the dataset collected and reviewed by the core lab. Similar analyses will be run on the VCI biomarker distributions for the Phase 2 subject group as was done in Phase 1. Additionally, subgroup analyses comparing biomarker results across research sites, and age groups, will be conducted to determine if any age or NovaGuide inter-operator variability effects are present in the data (two-way ANOVA with post-hoc comparisons).

Sample size calculation: In Phase 2, we seek to demonstrate stricter confidence bounds on biomarker diagnostic performance in excess of 90% ROC-AUC. Assuming the biomarker is observed to meet that performance threshold, then a sample of approximately 150 LVO subjects in each patient group is required to attain a one-tailed 95% confidence bound on the observed AUC of 3%. That is, the target AUC and sample size would afford 95% confidence that the underlying general population AUC is greater than 87%. Moreover, across five sites, this results in approximately 30 LVO subjects per site, affording sufficient power for detection of moderate potential inter-site effects in the range of Cohen’s $D \geq 0.75$.

Calculate study and site specific stroke workflow times: Stroke workflow parameters and times are well characterized in literature, including “Get with the Guidelines, Stroke” published by the American Heart Association, Inc. and will be utilized as a historical control comparator for data collected in Phase 2. We will use these published stroke guidelines which have mean times for the stroke workflow parameters to show that we are non-inferior to these when using the NovaGuide device. Additionally, the data will be compared to the corresponding randomized group (Cohort C and D)

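### The Phase 2 no-delay claim is tied to published mean times, gives the randomised No-TCD groups no deciding role, counts times that scanning cannot change, and has no margin, alpha or any/all rule.

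*Combined protocol and SAP*

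**What the plan says.** Under the heading "Phase 2 Primary Safety Endpoint", section 4.2.2 lists seven items. The first is "Incidence of device-related serious adverse events". The other six are times: last known normal to arrival, door to CT, door to IV-tPA, door to CTA, door to groin puncture, and CTA to groin puncture. Section 4.2.1 gives the same list for Phase 1.

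Section 11.1 gives the purpose of the workflow data: "This will enable us to demonstrate that the system does not adversely affect standard of care for subjects suspected of stroke". The Phase 1 comparators are literature, national and site metrics, and also the randomised Cohorts C and D.

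For Phase 2, section 11.2 treats the published times as a historical control and uses their "mean times for the stroke workflow parameters to show that we are non-inferior to these when using the NovaGuide device". It then adds: "Additionally, the data will be compared to the corresponding randomized group (Cohort C and D". Non-inferiority is attached to the published figures only. The randomised comparison has no stated test, margin or role in the conclusion.

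Neither section gives an alpha, a margin, a lead time, a lead comparator, or a rule on whether one time or all times must pass. The success criteria in section 11.5 concern VCI performance only.

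**The concern.** Randomising to TCD or No TCD is what allows this study to say whether scanning delays care. A comparison with published means cannot separate a scan effect from differences between these sites and the published ones. A site that is faster than the published mean could lose time to the scan and still look non-inferior. A slower site could fail although the scan cost nothing.

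The six times are also not interchangeable. Under the sequence in sections 4.6, 4.9 and 4.16.2, a delay caused by scanning an LVO patient falls on the interval from CTA to groin puncture. It cannot appear in arrival, CT or CTA times. With no rule on which time decides, several favourable primary results could be reported while the one interval that carries the delay fails.

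**Working it through.** **No plan figure to reproduce.** The documents give no sample size, power, margin or error rate for the workflow comparisons. The alpha of 0.05 in section 11.1 belongs to the VCI group difference, and the one-tailed 95% bound in section 11.2 belongs to the AUC. One-sided 5% is therefore my assumption below.

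**Step 1. Which times can a scan affect?** Cohort entry needs the CTA result (sections 4.6.1 and 4.6.2). Randomisation follows full eligibility and consent (4.9). The Cohort A scan follows CTA and precedes treatment such as thrombectomy, and tPA may already have been given (4.16.2). On that sequence:

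| Time | Can the scan change it? |
|---|---|
| Last known normal to arrival | No, before randomisation |
| Door to CT | No, before randomisation (time of CT is a balancing factor in 4.9) |
| Door to CTA | No under 4.6, 4.9 and 4.16.2 |
| Door to IV-tPA | Only if tPA comes after the scan |
| Door to groin puncture | Yes |
| CTA to groin puncture | Yes |

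Section 11.1 instead describes device use while the patient waits for CTA or intervention. That conflicts with 4.16.2 and leaves the door-to-CTA row open until the two are reconciled.

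**Step 2. How easily do the unaffected times pass?** Inputs: 156 per arm in Phase 2 (synopsis), true difference 0, one-sided 5%, margin expressed as a fraction m of the SD (assumed). For a two-arm comparison of means,

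P(pass) = Φ(m × √(n/2) − 1.645), with √(156/2) = 8.832.

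- m = 0.25: Φ(2.208 − 1.645) = Φ(0.563) = 71.3%.
- m = 0.50: Φ(4.416 − 1.645) = Φ(2.771) = 99.7%.

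At m = 0.25, at least one of the three passes with probability 1 − (1 − 0.713)³ = 97.6% if they are independent, and about 84% at correlation 0.8 (simulation). These are correct non-inferiority results for those times, but they say nothing about the effect of the scan.

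**Step 3. What would the false no-delay rate be for the affected times?** Set the true delay exactly at the margin for each affected time, test each against one comparator at one-sided 5%, and let ρ be the correlation between test statistics. For ρ = 0, P(at least one passes) = 1 − 0.95^k. Other values come from simulated equicorrelated normal statistics.

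| Times tested | ρ = 0 | ρ = 0.5 | ρ = 0.8 | ρ = 0.9 |
|---|---|---|---|---|
| Two puncture times, any passes | 9.75% | 8.8% | 7.5% | 6.8% |
| Two puncture times, both pass | 0.25% | 1.2% | 2.5% | 3.2% |
| Adding door-to-tPA, any passes | 14.3% | 11.9% | 9.2% | 8.0% |
| Adding door-to-tPA, all pass | 0.01% | 0.5% | 1.6% | 2.5% |

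The two puncture times share the CTA-to-groin interval, so the higher correlations are the more plausible for them. Under an all-must-pass rule the rate stays below 5% throughout.

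**The case against.** The strongest reply is that the plan defines no procedure whose error could be inflated. Without a margin and an alpha, a non-inferiority type I error does not exist. Nothing says that one passing time is enough: section 11.1 speaks of showing that nothing is delayed, and section 11.2 speaks of the parameters as a group. Both lean towards requiring all times to pass, which does not inflate error. The study's success criteria do not depend on the workflow claim.

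Most of this stands. A reader might infer that six primary times with several comparators put the no-delay claim at 2 to 5 times a 5% error rate. The documents do not support that. It takes an any-one-passes rule that is nowhere stated and an alpha borrowed from another analysis. It also counts three times that a scan cannot change, for which passing against Cohort C or D is not an error. For the two puncture times alone the any-pass rate is 6.8% to 9.75%, or 1.4 to 1.95 times 5%.

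The reply does not remove three gaps. A leaning is not a rule. The missing margin and alpha are themselves the more basic defect. And the non-inferiority statement still rests on a historical comparator when a randomised one is available.

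**Conclusion.** The point holds as a gap in specification and a weak choice of comparator, not as a demonstrated error rate. From the documents alone: six times are primary safety endpoints, non-inferiority is tied to published means, Cohorts C and D have no deciding role, and no margin, alpha or any/all rule is given. That three of the six times are fixed before scanning follows from sections 4.6, 4.9 and 4.16.2; for door-to-CTA it is subject to the conflict with section 11.1.

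The figures are conditional. The 71% and 99.7% pass rates assume 156 per arm, one-sided 5%, no true difference, and margins of 0.25 and 0.5 SD. The false no-delay rates of about 7% to 10% (two puncture times, correlation 0.9 to 0) and 9% to 14% (with door-to-tPA, correlation 0.8 to 0) assume that any single time may decide against one comparator at 5%. This should be corrected, because it concerns a primary safety endpoint and the evidence needed is already being collected.

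**What to change.** In sections 4.2.2 and 11.2:

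1. Keep device-related serious adverse event incidence as a primary safety endpoint.
2. Rest the no-delay conclusion on one randomised contrast: CTA acquisition to groin puncture, Cohort A (TCD) versus Cohort C (No TCD). State the non-inferiority margin and the one-sided alpha in advance. Puncture times exist only for patients who reach puncture, so state the analysis population and set the margin knowing that at most 156 per arm contribute.
3. Test door-to-groin puncture next, at the same alpha, only if the first contrast passes.
4. Report the other four times, Cohort B versus D, and all comparisons with published, national or site figures as supportive and descriptive.
5. Reconcile the scan timing in section 11.1 with section 4.16.2, since this decides whether door-to-CTA can be affected.

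The cost is wording only, with no new data or patients. The downside is that fewer workflow times can be called primary non-inferiority results.

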11.3 Imaging Core Lab Analysis

All imaging data will be sent to a core laboratory which will provide independent quantitative and qualitative assessment of all study data. They will be blinded to the study and radiology report data and provide independent review.

11.4 TCD Data Analysis

All TCD data acquired by the NovaGuide System will be sent to NovaSignal which will provide independent quantitative assessment of all TCD study data. They will be blinded to the study and radiology report data and provide independent review.

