1 PROTOCOL SYNOPSIS

Protocol Synopsis:	
Study Sponsor: NovaSignal Corp. [name] National Institute of Health (NIH)	Protocol No.: NA-01STR-03 Regulatory Class: II Study Device(s): NovaGuide and/or Lucid TCD System Development Phase: Phase 1: Feasibility; Phase 2: Pivotal
Study Title: Evaluate a NeXt Generation Portable Diagnostic Platform for Determination and Immediate Triage of Emergency Large Vessel Stroke (EXPEDITE IIA)	
Overall Study Design: This study is a multi-center, multi-phase, multi-cohort, prospective, randomized, open, blinded endpoint (PROBE), non-significant risk (NSR) device study including up to 420 evaluable subjects measured with the study device(s).	
Objective: The purpose of this study is to collect robust data from the robotic NovaGuide device or the Lucid TCD device to validate the Velocity Curvature Index (VCI) as a diagnostic biomarker tool to drive clinical decision making for assessing cerebral vascular occlusions confirmed by standard of care Computed Tomography Angiography (CTA) imaging.	
Number of Subjects: Phase 1: Up to 216 (54 Cohort A TCD, 54 Cohort A No TCD) (54 Cohort B TCD, 54 Cohort B No TCD) Phase 2: Up to 624 (156 Cohort A TCD, 156 Cohort A No TCD) (156 Cohort B TCD, 156 Cohort B No TCD)	Number of Sites: Phase 1: Up to 3 sites Phase 2: Up to 5 sites
Duration of Study Participation: 
Phase 1 Enrollment: 18 monthsPhase 2 Enrollment: 24 monthsTotal Study Duration: 1 to 7 days	
Phase 1 Study Design	
Phase 1 will include up to 54 subjects enrolled in Cohort A and 54 subjects enrolled in Cohort B. An interim feasibility and safety assessment will be completed after Phase 1.	
Phase 1 and Phase 2 Entry Criteria:	
Cohort A LVO	
Inclusion Criteria	

Subject aged 18 years and olderLarge vessel occlusion of the intracranial ICA, MCA (M1, M2), or multiple areas of the aforementioned locations confirmed by computed tomography angiography (CTA)Subject or Legally Authorized Representative has the ability to provide informed consent and comply with the protocol.	
Exclusion Criteria	

Head CT findings consistent with acute primary intracranial hemorrhage (SAH, ICH, etc.)Hemodynamically unstable patients requiring pharmacological support for hypertension	

Protocol Synopsis:	

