TCD Data Analysis: All TCD data acquired by the NovaGuide Robotic System or the Lucid M1 System (manual TCD) will be sent to NovaSignal which will provide independent quantitative and qualitative assessment of all study data. They will be blinded to the study and radiology report data and provide independent review.	
Data Analysis: Evaluation of correlation between diagnostic imaging standard of care and VCI biomarker by an independent core laboratory masked to local radiology determination. Success criteria will include clinical validation of VCI biomarker for LVO detection threshold performance at or exceeding 90% ROC-AUC (targeting SEN & SPE greater than 90%) to standard of care imaging.	

Phase 1 & 2 Schedule of Assessments				
Assessments	Cohort A¹ LVO TCD	Cohort B² Non-LVO TCD	Cohort C³ LVO NO TCD	Cohort D³ Non-LVO NO TCD
Informed Consent	X	X	X	X
Medical History	X	X	X	X
NIH Stroke Scale♦	X	X	X	X
Non-Contrast CT♦	X	X	X	X
CT Angiography♦	X	X	X	X
Cohort Assignment	X	X	X	X
Randomization TCD / No TCD	X	X	X	X
TCD Scan (NovaGuide or Lucid)	X	X		
Device-Related Adverse Events	X	X		
Concomitant Medications	X	X		

♦ Standard of Care

1. Cohort A LVO TCD subjects scans will be collected following CTA within a three (3) hour window, prior to treatment (e.g. mechanical thrombectomy).
2. Cohort B Non-LVO TCD subjects scans will be collected within a 24-hour period after enrollment.
3. If randomized to 'No TCD' group in either Cohort, TCD scan will not be conducted, but still followed through to discharge.

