4.16.2 Lucid M1 System Scanning Technique (Traditional TCD)

If traditional TCD is conducted using the Lucid M1 System alone, measurements will be collected in the MCA at multiple depths ranges between 45 to 65 mm. The MCA scans will be collected from the trans-temporal window by positioning the probe superior to the zygomatic arch. Once cerebral blood flow velocity (CBFV) of the target vessel is found, the TCD operator will hold this position to record 30 seconds of data.

Cohort A TCD will be subjects identified per CTA findings in the Emergency Room (ER), Stroke Care Unit or Imaging Unit as having a large vessel occlusion. A single TCD scan will be collected by a designated TCD operator using the NovaGuide System or the Lucid M1 System alone (manual TCD). The TCD scan will be collected following CTA within a three (3) hour window and prior to standard of care stroke treatment (e.g., mechanical thrombectomy). Note, tPA can be administered prior to TCD measurements. Study measurements will not delay nor interfere with the patients' standard of care treatment. No follow-up scans will be collected.

Cohort B TCD will be subjects identified per CTA findings in the Emergency Room (ER), Stroke Care Unit or Imaging Unit as having a non-large vessel occlusion. A single TCD scan will be collected by a designated TCD operator using the NovaGuide Robotic System or the Lucid M1 System alone (manual TCD). These scans will be collected within a 24-hour period after enrolment and no follow-up scans will be collected.

Cohort C NO TCD will be subjects identified per CTA findings in the Emergency Room (ER), Stroke Care Unit or Imaging Unit as having a large vessel occlusion. No TCD scans will be conducted and subjects followed through to discharge.

Cohort D NO TCD will be subjects identified per CTA findings in the Emergency Room (ER), Stroke Care Unit or Imaging Unit as having a non-large vessel occlusion. No TCD scans will be conducted and subjects followed through to discharge.

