7.3 Reporting Adverse Events

Device-related adverse events information will be collected throughout the study. From the initiation of and end of device use, all subjects scanned with the NovaGuide System shall be assessed for any potentially device related complications or adverse events. All events shall be followed until resolution or through the end of a subject's study participation.

Event, onset date, severity, relatedness, device relationship, treatment and outcome of the AE will be recorded on the appropriate case report form. Any device-related AEs will be monitored until they are adequately resolved or explained. This classification of the event determines the reporting procedures to be followed. For purposes of this protocol, the following definitions will apply.

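### The analysis and adverse-event text names only NovaGuide although TCD subjects may be scanned with Lucid M1 alone, and no by-device analysis is planned if both are pooled

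*Combined protocol and SAP*

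**What the plan says.** The synopsis lists "Study Device(s): NovaGuide and/or Lucid TCD System". The scan row of the schedule of assessments (4.15) names either device. Section 4.16.2 lets the operator use NovaGuide or Lucid alone in both the LVO and the non-LVO TCD cohorts, and gives no rule for choosing.

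On analysis, the synopsis reads "All TCD data acquired by the NovaGuide Robotic System or the Lucid M1 System (manual TCD) will be sent to NovaSignal". The matching sentence in 11.4 drops the manual system: "All TCD data acquired by the NovaGuide System will be sent to NovaSignal". Yet it goes on to promise "independent quantitative assessment of all TCD study data". Section 11.1 computes VCI for each subject. It introduces the three guideline workflow percentages with "We will calculate the following for subjects that have NovaGuide measurements".

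On safety, section 7 has events recorded when they are suspected to be related to NovaGuide. The end of section 7 assesses subjects who have NovaGuide data of adequate quality. Section 7.3 says "all subjects scanned with the NovaGuide System shall be assessed for any potentially device related complications or adverse events". The schedule, by contrast, ticks device-related adverse events for both TCD cohorts with no device restriction, and the serious-event row in section 8 refers to the study device.

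Device is not among the balancing factors in 4.9. The only subgroup factors in 11.2 are site and age.

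**The concern.** The documents give at least two answers to two basic questions: whose scans enter the diagnostic analysis, and who is assessed for adverse events. No passage says which text takes precedence.

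For safety, the three NovaGuide-only statements differ from each other as well as from the schedule. The statement at the end of section 7 is the narrowest. It ties adverse-event assessment to data quality, so a difficult or failed scan would remove the subject from the set in which events are sought.

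For the diagnostic endpoint, including both devices removes the conflict but opens a second gap. NovaGuide searches automatically and then monitors for up to 20 minutes (4.16.1). Lucid is hand-held and records 30 seconds (4.16.2). Section 2 says that the quality of technologist-acquired TCD data varies by user, and 5.3 counts on automation to reduce that influence. The scan windows also differ: three hours after CTA and before treatment for the LVO cohort, 24 hours after enrolment for the non-LVO cohort. Device use could therefore differ between the groups that the AUC compares, and the plan has no analysis that would show it.

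**Working it through.** **1. Passages side by side**

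| Topic | Either device | NovaGuide only |
|---|---|---|
| Scan | Synopsis, 4.15, 4.16.2 | none |
| Data sent for analysis | Synopsis; closing words of the 11.4 sentence | Opening words of the same sentence |
| VCI computed | 11.1, each subject | none |
| Workflow percentages | none | 11.1 |
| Adverse events | 4.15; section 8 serious-event row | 7 (recording), 7 (adequate-quality data), 7.3 (scanned) |

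**2. The plan's own precision figures.** Hanley-McNeil, with n per group, Q1 = A/(2−A) and Q2 = 2A²/(1+A):

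SE² = [A(1−A) + (n−1)(Q1−A²) + (n−1)(Q2−A²)] / n²; one-sided 95% bound = 1.645 × SE.

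- Phase 2 (11.2): A = 0.90, Q1 = 0.8182, Q2 = 0.8526. At n = 150, SE = 0.0185, the bound is 3.04 points and the lower limit 87.0%. The stated 3% and 87% reproduce.
- Phase 1 (11.1): A = 0.85, n = 50. SE = 0.0391, the bound is 6.4 points and the lower limit 78.6%. The stated bound below 7%, and the margin over 78%, reproduce.

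**3. If Lucid scans were left out.** The share scanned with Lucid alone is not given; 20% and 40% are assumptions. Starting from the enrolment targets of 156 and 54 per group:

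| Assumed Lucid share | Phase 2 n | Bound | Lower limit | Phase 1 n | Bound |
|---|---|---|---|---|---|
| 0% | 156 | 2.98 | 87.0% | 54 | 6.2 |
| 20% | 125 | 3.33 | 86.7% | 43 | 6.9 |
| 40% | 94 | 3.84 | 86.2% | 32 | 8.1 |

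The Phase 1 bound reaches 7 points at 42 per group, a Lucid share of 1 − 42/54 = 22%.

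**4. Safety denominator.** Scanned subjects over both phases: 2×54 + 2×156 = 420. At 20% or 40% Lucid, NovaGuide-scanned subjects number 336 or 252. With zero events the one-sided 95% upper limit is 1 − 0.05^(1/n): 0.71% at 420, 0.89% at 336 and 1.18% at 252.

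**5. Pooling.** The effect depends on the Lucid share in each cohort, the VCI shift between devices and its sign; the documents give none of these. As an illustration with wholly assumed inputs, take 60% Lucid in LVO, 20% in non-LVO and a shift of 0.5 SD. An AUC of 0.85 corresponds to a separation d = √2 × Φ⁻¹(0.85) = 1.466 SD. The mixture AUC is the sum, over the four device pairings, of pairing probability × Φ((d + shift difference)/√2). It is 0.875 if the shift widens the separation and 0.81 if it narrows it.

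**The case against.** The best defence is that 11.4 is a shortened copy of the synopsis sentence. It says where data go, not who is analysed, and ends by covering all TCD data. NovaGuide is itself the Lucid M1 plus a robotic accessory, and 4.19 stores TCD data on the NovaGuide System, so the name is used loosely. This stands. A reader might infer from 11.4 that Lucid subjects are excluded from the VCI analysis, but the documents do not support that: no passage excludes them, and the synopsis and 11.1 point the other way.

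A reader might also infer that the NovaGuide restriction in 11.1 breaks the randomised comparison. It introduces three guideline percentages. The comparison with Cohorts C and D is a separate sentence in 11.1, and again in 11.2, and neither limits it to NovaGuide subjects. What remains is that neither says the comparison is by randomised arm.

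On safety, the endpoint in 4.2 is not restricted by device, and causality in 7.3.2 is rated against the study device. Emphasis on NovaGuide is understandable because it is the investigational component. Even so, the operative assessment sentences in 7 and 7.3 name NovaGuide subjects only, and the data-quality condition in 7 has no such explanation.

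On pooling, VCI needs only 15 seconds of waveform (3.5), both methods search at 45 to 65 mm, and both use the Lucid M1. Recording length alone therefore need not alter VCI. That stands against any claim that a device effect exists or inflates the AUC. It does not remove the case for looking, since section 2 itself says that quality varies by user.

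**Conclusion.** The conflict between passages is real and should be reconciled. The firmest part is safety: followed literally, sections 7 and 7.3 omit Lucid-only subjects, and the end of section 7 also omits subjects with poor-quality scans, against a schedule that requires device-related events in both TCD cohorts. For the VCI analysis, inclusion of both devices is the likelier intent. The gap is then that two acquisition methods, not allocated at random, are pooled with no by-device analysis.

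The precision cost of leaving Lucid scans out would be modest: at the assumed 20% to 40% share, the Phase 2 lower limit falls by 0.3 to 0.9 points (87.02% to 86.67% or 86.16% before rounding). Phase 2 success is worded as an AUC at or above 90%, so that limit does not by itself decide the trial. No stated figure in the plan is wrong because of this point. The size and direction of any device confounding cannot be derived from the documents; the illustration shows only that it could go either way.

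**What to change.** - Reconcile 7, 7.3 and 11.4 with the synopsis and schedule. TCD analysis should cover subjects scanned with either device. Adverse-event assessment should cover every subject scanned, or in whom a scan was attempted, with either device and regardless of data quality.
- In 11.1, extend the guideline percentages to subjects scanned with either device. In 11.1 and 11.2, state that the workflow comparison with Cohorts C and D is by randomised arm.
- Keep the pooled AUC as primary. Pre-specify, as supportive analyses, AUC, sensitivity and specificity for each device, and a device-stratified AUC (LVO against non-LVO within device, then combined). Report the number of scans by device and cohort.

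Replacing the pooled primary AUC with the stratified one is not needed; it would change the primary measure and could be unstable if one device is rare.

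The cost is wording and a small amount of extra analysis. Section 4.18 already collects device-use information, so no new data are required. The downside is wide device-specific intervals if one device is seldom used.
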